### **4.3 Benefit/Risk**

Subjects in clinical trials generally cannot expect to receive direct benefit from treatment during participation, as clinical trials are designed to provide information about the safety and effectiveness of an investigational medicine.

Additional details regarding specific benefits and risks for subjects participating in this clinical trial may be found in the accompanying Investigators Brochure (IB) and Informed Consent documents.

Beneficial effects of pembrolizumab have been seen in several trials to date. Publications of a significantly positive benefit/risk ratio have been reported for melanoma both in a single arm study encompassing nearly 1000 subjects (KN001), which led to USFDA approval in September 2014, and in a randomized comparison to chemotherapy (KEYNOTE-002 [KN002]— detailed in the IB). Additional potential benefits are addressed in section 4.1.3.1

which details responses of KN012 trial; a multi-cohort Phase Ib study of which one cohort enrolled subjects with recurrent or metastatic gastric or GEJ adenocarcinoma that expressed PD-L1 ( $\geq 1\%$  by immunohistochemistry). Although two-thirds of subjects had received at least two prior therapies for advanced disease, pembrolizumab monotherapy achieved an interim ORR of 33.3% by RECIST v.1.1 per investigator review (95% confidence interval (CI) (19.1%, 50.2%); all partial responses). The interim disease control rate (DCR) was 41% (95% CI (25.6%, 57.9%)), and the interim median duration of response was 24 weeks (range 8+ to 33+ weeks).

In KN012 the most common AEs included fatigue (17.9%), decreased appetite (12.8%), hypothyroidism (12.8%), and arthralgia (10.3%). Three Grade 3 AEs were observed, one each for peripheral sensory neuropathy, fatigue, and decreased appetite. In addition, one Grade 4 pneumonitis and one Grade 5 hypoxia were reported.

An early safety analysis will be performed to evaluate the safety of each treatment arm. This interim safety analysis will occur when at least 10 subjects from each arm (30 total subjects) have completed at least 1 cycle of treatment. The safety data will be submitted to an external DMC.

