All other immune-related AEs	Intolerable/persistent Grade 2	Withhold	
 
Based on type and severity of AE administer corticosteroids
 
	
 
Ensure adequate evaluation to confirm aetiology and/or exclude other causes
 

	Grade 3	Withhold or discontinue based on the type of event. Events that require discontinuation include and not limited to: Guillain-Barre Syndrome, encephalitis		
	Grade 4 or recurrent Grade 3	Permanently discontinue		

1. Withhold or permanently discontinue pembrolizumab is at the discretion of the investigator or treating physician.
 
NOTE:                      For subjects with Grade 3 or 4 immune-related endocrinopathy where withhold of pembrolizumab is required, pembrolizumab may be resumed when AE resolves to <math>\leq</math> Grade 2 and is controlled with hormonal replacement therapy or achieved metabolic control (in case of T1DM).
				

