## 6.0 TRIAL FLOW CHART

### 6.1 Initial Treatment Phase

#### 6.1.1 Treatment Arm 1: Pembrolizumab Monotherapy

Trial Period:	Screening Phase		Treatment Cycles a						End of Treatment	Post-Treatment		
Treatment Cycle	Tumour Tissue collection/submission	Screening	1	2	3	4	5	Cycle 6 and beyond	Last Dose	Safety Follow-up	Follow Up Visits b	Survival Follow-up c
									At time of treatment discon	30 days post discontinuation	Every 6 weeks post discontinuation	Every 12 weeks
Scheduling Window (Days) d :	-28 to -1	-21 to -1		± 3	± 3	± 3	± 3	± 3	± 3	± 7	± 7	± 7
Administrative Procedures												
Informed Consent e	X											
Informed Consent for Future Biomedical Research f	X											
Inclusion/Exclusion Criteria		X										
Subject Identification Card		X										
Demographics and Medical History		X										
Prior and Concomitant Medication Review g		X	X	X	X	X	X	X	X	X		
Clinical Procedures/Assessments												
Review Adverse Events h	X	X	X	X	X	X	X	X	X	X	X	
ePROs (HRQoL Measures) i			X	X	X	X	X	X i	X	X		
12-Lead ECG (Local)		X										
Full Physical Examination		X							X			
Directed Physical Examination			X	X	X	X	X	X				
Vital Signs and Weight j		X	X	X	X	X	X	X	X			
ECOG Performance Status n		X	X	X	X	X	X	X	X			
Post-study Anticancer Therapy Status											X	X
Survival Status c			←								→	X
Trial Treatment Administration												
Pembrolizumab k			X	X	X	X	X	X				
Laboratory Procedures/Assessments: Analysis performed by LOCAL												

Trial Period:	Screening Phase		Treatment Cycles a						End of Treatment	Post-Treatment		
Treatment Cycle	Tumour Tissue collection/submission	Screening	1	2	3	4	5	Cycle 6 and beyond	Last Dose	Safety Follow-up	Follow Up Visits b	Survival Follow-up c
									At time of treatment discon	30 days post discontinuation	Every 6 weeks post discontinuation	Every 12 weeks
Scheduling Window (Days) d :	-28 to -1	-21 to -1		± 3	± 3	± 3	± 3	± 3	± 3	± 7	± 7	± 7
laboratory												
Pregnancy Test – Serum or Urine l		X	X	X	X	X	X	X		X		
PT/INR and aPTT m		X										
CBC with Differential n		X		X	X	X	X	X	X	X		
Chemistry Panel n		X		X	X	X	X	X	X	X		
Urinalysis n		X										
T3(or Free T3), FT4 and TSH n		X		X		X		X		X		

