- u. In subjects who discontinue study therapy without centrally verification of disease progression, a radiologic evaluation should be performed at the time of treatment discontinuation (ie, date of discontinuation  $\pm 4$ -week window). If a previous scan was obtained within 4 weeks prior to the date of discontinuation, then a scan at treatment discontinuation is not required. These subjects should be assessed every 6 weeks ( $42 \pm 7$  days) by radiologic imaging to monitor disease status until the start of new anti-cancer therapy, disease progression determined by the central imaging vendor, death, or end of study.
- v. Baseline tumour tissue for biomarker analysis from newly obtained core or excisional biopsy (FNA not adequate) and archival tissue sample (where available) should be tested for PD-L1. Only PD-L1 positive subjects will be eligible for this trial. Tumour submission can occur up to 28 days prior to randomization. Consent must be obtained prior to tumour tissue submission/collection. Detailed instructions for tissue collection, process and shipment are provided in the Procedures Manual. If the subject signs the Future Biomedical Research (FBR) consent, any leftover tissue that would ordinarily be discarded at the end of the main study will be retained for FBR. An optional newly obtained core or excisional biopsy (FNA not adequate) can be collected at Discontinuation for PD. This biopsy is requested but not required. Endoscopic biopsies are permitted
- w. Full physical exam and directed physical exam will include neurologic exam to be performed by the treating physician or designee. Audiometry testing will be performed at baseline, and is repeated during the study as clinically indicated per the treating physician or designee.
- x. After documented local site assessed disease progression, or the start of new anticancer treatment; contacts are approximately every 12 weeks by telephone. Updated survival status may be requested by the Sponsor at any time during the course of the study. Upon Sponsor notification, all subjects who do not/will not have a scheduled study visit or study contact during the Sponsor defined time period will be contacted for their survival status (excluding subjects that have a death event previously recorded).

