#### **7.1.2.2.2 Directed Physical Exam**

For cycles that do not require a full physical exam as defined in Section 6, the investigator or qualified designee will perform a directed physical exam as clinically indicated prior to the administration of the trial treatment. New clinically significant abnormal findings should be recorded as AEs.

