### **7.2.4 Evaluating Adverse Events**

An investigator who is a qualified physician will evaluate all adverse events according to the NCI Common Terminology for Adverse Events (CTCAE), version 4.0. Any adverse event which changes CTCAE grade over the course of a given episode will have each change of grade recorded on the adverse event case report forms/worksheets.

All adverse events regardless of CTCAE grade must also be evaluated for seriousness.

For studies in which multiple agents are administered as part of a combination regimen, the investigator may attribute each adverse event causality to the combination regimen or to a single agent of the combination. In general, causality attribution should be assigned to the combination regimen (i.e., to all agents in the regimen). However, causality attribution may be assigned to a single agent if in the investigator's opinion, there is sufficient data to support full attribution of the adverse experience to the single agent.

Table 11 Evaluating Adverse Events

An investigator who is a qualified physician, will evaluate all adverse events as to:

V4.0 CTCAE Grading	Grade 1	Mild; asymptomatic or mild symptoms; clinical or diagnostic observations only; intervention not indicated.
	Grade 2	Moderate; minimal, local or noninvasive intervention indicated; limiting age-appropriate instrumental ADL.
	Grade 3	Severe or medically significant but not immediately life-threatening; hospitalization or prolongation of hospitalization indicated; disabling; limiting self-care ADL.
	Grade 4	Life threatening consequences; urgent intervention indicated.
	Grade 5	Death related to AE

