## 8.6.2 Statistical Methods for Safety Analyses

Safety and tolerability will be assessed by clinical review of all relevant parameters including adverse experiences (AEs), laboratory tests, vital signs, etc.

The analysis of safety results will follow a tiered approach (Table 14). The tiers differ with respect to the analyses that will be performed. Safety parameters or adverse experiences of special interest that are identified *a priori* constitute “Tier 1” safety endpoints that will be subject to inferential testing for statistical significance with p-values and 95% confidence intervals provided for between-group comparisons. Other safety parameters will be considered Tier 2 or Tier 3. Tier 2 parameters will be assessed via point estimates with 95% confidence intervals provided for between-group comparisons; only point estimates by treatment group are provided for Tier 3 safety parameters.

Adverse experiences (specific terms as well as system organ class terms) and predefined limits of change in laboratory, vital signs, and ECG parameters that are not pre-specified as Tier-1 endpoints will be classified as belonging to "Tier 2" or "Tier 3", based on the number of events observed. Membership in Tier 2 requires that at least 4 subjects in any treatment group exhibit the event; all other adverse experiences and predefined limits of change will belong to Tier 3.

The threshold of at least 4 events was chosen because the 95% confidence interval for the between-group difference in percent incidence will always include zero when treatment groups of equal size each have less than 4 events and thus would add little to the interpretation of potentially meaningful differences. Because many 95% confidence intervals may be provided without adjustment for multiplicity, the confidence intervals should be regarded as a helpful descriptive measure to be used in review, not a formal method for assessing the statistical significance of the between-group differences in adverse experiences and predefined limits of change.

Continuous measures such as changes from baseline in laboratory, vital signs, and ECG parameters that are not pre-specified as Tier-1 endpoints will be considered Tier 3 safety parameters. Summary statistics for baseline, on-treatment, and change from baseline values will be provided by treatment group in table format.

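### A neurologic exam is required at physical exams in Arms 2 and 3 but not in Arm 1, so examination-detected nervous-system AEs are sought unequally in the monotherapy versus SOC safety comparison

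*Combined protocol and SAP*

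**What the plan says.** In the flow chart for Arms 2 and 3 (6.1.2), footnote w is attached to both physical-exam rows: "Full physical exam and directed physical exam will include neurologic exam to be performed by the treating physician or designee". The same footnote adds: "Audiometry testing will be performed at baseline, and is repeated during the study as clinically indicated per the treating physician or designee".

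The Arm 1 flow chart (6.1.1) has the corresponding rows, including "Directed Physical Examination", with X marks at the same visits. Neither row carries a footnote, and footnotes a to t mention neither a neurologic exam nor audiometry.

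Section 7.1.2.2 applies to all arms. It describes a complete exam at screening and a directed exam whose conduct is left to clinical indication, and names no neurologic component for either. On the directed exam it says: "New clinically significant abnormal findings should be recorded as AEs". The full-exam text has a matching rule for findings after the first dose. In Table 11 (7.2.4), Grade 1 covers "asymptomatic or mild symptoms; clinical or diagnostic observations only; intervention not indicated".

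Section 8.6.2 and Table 14 give 95% confidence intervals for between-treatment differences in specific AEs and system organ classes, with this threshold: "Membership in Tier 2 requires that at least 4 subjects in any treatment group exhibit the event". There is no restriction by grade for specific terms and no remark on differing examination content.

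**The concern.** Two arms that are compared on AE incidence should be looked at equally hard for those AEs. Here the protocol fixes a neurologic exam in the SOC arm and leaves it to judgement in the monotherapy arm. A sign found only on examination, such as reduced distal sensation that the subject has not reported, is then more likely to enter the database in Arm 3 than in Arm 1. The pull is in one direction, towards a cleaner nervous-system profile for monotherapy.

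Neurologic events are not confined to cisplatin. Table 5 lists "Guillain-Barre Syndrome, encephalitis" among immune-related events on pembrolizumab, and the Grade 3 events in the gastric monotherapy cohort (4.3) were "one each for peripheral sensory neuropathy, fatigue, and decreased appetite". Safety and tolerability is a stated secondary objective (3.2). Monotherapy versus SOC carries hypotheses H4 to H6, and relative tolerability would weigh in reading a non-inferiority result under H4.

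**Working it through.** The plan gives no figure on this point, so there is nothing to reproduce. The check is a comparison of the two initial-phase charts with the general text.

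| Element | Arm 1 (6.1.1) | Arms 2 and 3 (6.1.2) |
|---|---|---|
| Full exam | Screening, end of treatment | Same |
| Directed exam | Each treatment cycle | Same |
| Neurologic component | None named | Footnote w, both rows |
| AE review | Screening through follow-up visits | Same |
| New clinically significant finding after dosing | AE | AE |

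1. **Content.** The wording in 7.1.2.2.2 that leaves the directed exam to clinical indication covers all arms. In Arms 2 and 3, footnote w then fixes what the exam must contain. In Arm 1 nothing does, so a neurologic exam there depends on the investigator.

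2. **From finding to AE.** The rule is the same in all arms. Because Grade 1 includes observations without symptoms, a clinically significant sign can be an AE on examination alone.

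3. **From AE to comparison.** Four subjects with a term in any one arm are enough for a between-treatment interval at any grade. Section 8.6.2 does not set nervous-system terms apart.

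4. **Direction.** Let π1 and π3 be the true incidences in Arms 1 and 3, and d1 and d3 the probabilities that a true event is recorded. The expected recorded difference, Arm 1 minus SOC, is π1·d1 − π3·d3 = d3·(π1 − π3) − π1·(d3 − d1). The last term is the ascertainment part. If d1 is below d3 it lowers the recorded difference and favours monotherapy. Its size, π1·(d3 − d1), needs quantities that the documents do not give.

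5. **Screening.** Footnote w sits on the full-exam row, which includes screening (days -21 to -1). Randomisation follows screening (5.3, 7.1.5.1), so a site cannot know which chart applies. Examining everyone goes beyond 6.1.1; examining no one breaches 6.1.2. The neurologic baseline against which a later finding is judged new may therefore differ between sites.

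6. **What is not touched.** Arms 2 and 3 share one chart, so their comparison is balanced. OS does not depend on this exam, and PFS rests on blinded central imaging and death.

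**The case against.** The case against is substantial, and much of it stands.

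- **Arm 1 is still observed.** It has AE review and physical exams at the same visits, and all AEs from randomisation to 30 days after treatment must be reported (7.2). A reader might infer that neurologic events are not sought in Arm 1 at all. The documents do not support that; the difference is one of intensity.
- **Hearing.** A reader might extend the point to ototoxicity, since footnote w mentions audiometry. Only the baseline test is mandatory, and it cannot detect a treatment-emergent event. Repeats are driven by clinical indication. No arm has a systematic on-treatment hearing search.
- **Filter.** Only clinically significant findings become AEs, in every arm, which removes many trivial signs. The pembrolizumab examples above are severe events. They show that neurologic toxicity occurs on monotherapy, not that mild cases are missed.
- **Size.** A reader might infer that the asymmetry would by itself yield intervals excluding zero. That needs assumed inputs near an extreme. Take about 250 per arm (750/3), an assumed true incidence of 20% in both arms, complete recording in SOC (50 events), and Miettinen-Nurminen 95% intervals. Missing 10% in Arm 1 (45 events) gives 2.0 points (-4.9 to 8.9). Missing 30% (35 events) gives 6.0 points (-0.6 to 12.6). Only at 40% (30 events) is zero excluded: 8.0 points (1.6 to 14.4). The 20% is itself doubtful: the most frequent AE listed for the gastric monotherapy cohort is fatigue at 17.9% (4.3).
- **Status of the intervals.** Section 8.6.2 calls them a descriptive aid, not a formal assessment of significance, and there are no Tier 1 events.
- **Rationale.** Table 7 has its own row for ototoxicity or sensory neuropathy on cisplatin, so extra monitoring in Arms 2 and 3 is reasonable.

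The rationale explains why the chemotherapy arms are examined. It does not explain comparing Arm 1 with them under a lighter exam without saying so. Examining everyone at screening would balance the baseline, but 6.1.1 does not ask for it.

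**Conclusion.** The asymmetry is real, and so is the inconsistency at screening. The Arm 1 versus SOC comparison of nervous-system AEs may be biased in favour of monotherapy, mainly through low-grade findings that surface on examination. The size cannot be estimated from the documents and could be negligible. The conclusion assumes that sites follow the two charts as written; where investigators already do a neurologic exam in Arm 1, the bias shrinks accordingly. The comparison is descriptive and no hypothesis from H1 to H7 is affected. This is an inexpensive improvement to a secondary safety comparison, not a threat to the trial's conclusions.

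**What to change.** 1. Reconcile 6.1.1, 6.1.2 and 7.1.2.2 so that the neurologic component of the scheduled full and directed exams is the same in all arms, including the common screening exam before allocation. Audiometry need not change for this purpose.
2. In 8.6.2, add a display of Arm 1 versus SOC nervous-system terms at Grade 2 or higher, where recording should depend less on a directed exam. Grades and grade changes are already recorded (7.2.4), so no new data are needed.
3. Add one sentence to 8.6.2 stating that any-grade nervous-system differences between Arm 1 and SOC are subject to unequal ascertainment.

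The cost is a few minutes within exams already scheduled in Arm 1, a few more Grade 1 AEs recorded there, and one extra table. For visits that have already taken place the first step cannot help, but the second and third still can.

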**6.2 Second Course Phase (Retreatment with Pembrolizumab)**

Trial Period:	Treatment Cycles a						End of Treatment	Post-Treatment		
Treatment Cycle:	1	2	3	4	5	Cycle 6 and beyond	Last Dose	Safety Follow-up	Follow Up Visits b	Survival Follow-up c
							At time of treatment discon	30 days post discontinuation	Every 6 weeks post discontinuation	Every 12 weeks
Scheduling Window (Days) d :	-3	± 3	± 3	± 3	± 3	± 3	± 3	± 7	± 7	± 7
Administrative Procedures										
Eligibility Criteria e	X									
Concomitant Medication Review f	X	X	X	X	X	X	X	X		
Clinical Procedures/Assessments										
Review Adverse Events g	X	X	X	X	X	X	X	X	X	
Full Physical Examination	X						X			
Directed Physical Examination		X	X	X	X	X				
Vital Signs and Weight h	X	X	X	X	X	X	X	X		
ECOG Performance Status k	X	X	X	X	X	X	X			
Pembrolizumab Administration	X	X	X	X	X	X				
Post-study Anticancer Therapy Status									X	X
Survival Status n	←								→	X
Laboratory Procedures/Assessments: Analysis performed by LOCAL laboratory										
Pregnancy Test – Urine or Serum i	X	X	X	X	X	X		X		
PT/INR and aPTT j	X									
CBC with Differential k	X	X	X	X	X	X k	X	X		
Chemistry Panel k	X	X	X	X	X	X k	X	X		
Urinalysis k	X									
T3(or Free T3), FT4 and TSH k	X		X		X			X		
Efficacy Measurements										
Tumour Imaging l	X		X		X	X	X m		X m	

- a. In general, assessments/procedures are to be performed on Day 1 and prior to the first dose of treatment for each cycle unless otherwise specified. Treatment cycles are 3 weeks.
- b. In subjects who discontinue study therapy without documented disease progression, every effort should be made to continue monitoring their disease status by radiologic imaging every 6 weeks (42 ± 7 days) up to week 30 or every 9 weeks (± 7 days) if after Week 30, until (1) the start of new anti-cancer treatment, (2) disease progression as assessed by the central imaging vendor, (3) death, or (4) the end of the study, whichever occurs first.
- c. After the start of new anti-cancer treatment or documented disease progression by the central imaging vendor, the subject should be contacted by telephone every 12 weeks.

weeks to assess for survival status. The Sponsor may request survival status be assessed at additional time points during the course of the study. For example, these additional time points may be requested prior to; an eDMC safety review, efficacy interim analysis, and/or final analysis. All subjects who are not known to have died prior to the request for these additional survival status time points will be contacted at that time.

- d. In general, the window for each visit is  $\pm 3$  days unless otherwise noted.
- e. Subjects who either a) attain a CR and discontinue treatment or b) discontinue treatment after 35 administrations (approximately 2 years) on study treatment for reasons other than disease progression or intolerability may restart trial treatment if they meet the criteria specified in Section 7.1.5.2.1.
- f. Concomitant medications – Enter new medications started during the trial through the Safety Follow-up visit. Record all medications taken for SAEs as defined in Section 7.2.
- g. Record all AEs occurring within 30 days after the last dose of trial treatment. Report all SAEs (related and unrelated to trial treatment) and ECIs occurring up until 90 days after the last dose of trial treatment or 30 days after the end of treatment if the subject initiates new anticancer therapy, whichever occurs first. Afterwards, report only SAEs and ECIs that are related to trial treatment.
- h. Vital signs to include temperature, pulse, respiratory rate, weight and blood pressure.
- i. For women of reproductive potential, a serum pregnancy test should be performed within 72 hours prior to each cycle of trial treatment and 30 days post treatment. A urine test can be considered if serum is not appropriate. Pregnancy tests (serum and/or urine tests) should be repeated if required by local guidelines.
- j. Coagulation factors (PT/INR and aPTT) should be tested as part of the screening procedures for all subjects. And may be performed within 10 days prior to the first retreatment dose of pembrolizumab.
- k. ECOG PS for screening is to be performed within 3 days prior to the first dose of trial treatment. Laboratory tests for screening are to be performed within 10 days prior to the first dose of trial treatment. See Section 7.1.3 for details regarding laboratory tests. After Cycle 1, lab samples can be collected up to 72 hours prior to the scheduled time point. See Section 7.1.3 for details regarding laboratory tests. To be repeated every 2 cycles after Cycle 5. CBC with Differential, Chemistry panel, are to be repeated every 2 cycles after Cycle 6 (eg, Cycle 8-Day 1, Cycle 10-Day 1). Thyroid function tests should be collected every 6 weeks (every 2 cycles, eg, Cycles, 7, 9, 11, etc). Unresolved labs that are drug related AEs should be followed until resolution. Labs do not need to be repeated after the end of trial treatment if labs are within normal range.
- l. A scan must be performed within 21 days prior to restarting treatment with pembrolizumab. Imaging should continue to be performed every 6 weeks ( $42 \pm 7$  days) after the first dose of trial retreatment or more frequently if clinically indicated. Imaging timing should follow calendar days and should not be adjusted for any dose modifications. The exact same image acquisition and processing parameters should be used throughout the study.
- m. In subjects who discontinue study therapy without confirmed disease progression, a radiologic evaluation should be performed at the time of treatment discontinuation (ie, date of discontinuation  $\pm 4$ -week window). If a previous scan was obtained within 4 weeks prior to the date of discontinuation, then a scan at treatment discontinuation isn't mandatory
- n. After documented local site assessed disease progression, or the start of new anticancer treatment; contacts are approximately every 12 weeks by telephone. Updated survival status may be requested by the Sponsor at any time during the course of the study. Upon Sponsor notification, all subjects who do not/will not have a scheduled study visit or study contact during the Sponsor defined time period will be contacted for their survival status (excluding subjects that have a death event previously recorded).

